For those randomized to access to intensive treatment, the Tobacco Care Manager or UW-CTRI staffer will obtain oral assent to screen for current eligibility for varenicline and/or combination NRT (depending on their initial eligibility at enrollment—only the medications(s) for which the person met prerequisites at enrollment will be considered as options), will conduct this screening, and will then obtain oral consent to begin intensive treatment over the phone (see uploaded Treatment Initiation Screen and Consent). Those who were randomly assigned to receive incentives for treatment initiation will be reminded that they can earn \$40 by completing a first counseling call with a UW-CTRI quit coach. Medication and UW-CTRI health-counselor delivered telephone counseling will not be dispensed to patients unless they provide oral consent for intensive treatment. Medications also will not be dispensed until the patient's primary care provider has had a chance to review and decline a request for the patient to begin the medications for which they are eligible according to the study protocol. Because we: anticipate that not all participants will request smoking cessation treatment during the study, want medication screening to be done at the time of the smoking cessation attempt, and want to minimize burden on primary care providers, medication requests for combination NRT or varenicline will be sent to primary care providers only after a participant has requested intensive treatment, assented to and passed eligibility screening, and consented to intensive treatment over the phone. Those in the intensive treatment condition who are not eligible for either combination NRT or varenicline will still have access to 3 sessions of UW-CTRI quit coach counseling, as will those who are eligible but decline to use combination NRT or varenicline. Access to counseling is not dependent on medication eligibility or election. Adverse events will be assessed among all those who initiate stop-smoking treatment at phone follow-up interviews 3, 12, and 26 weeks post-target quit date. In addition, adverse events will be assessed among those in intensive treatment during the quit coach counseling calls 1 week pre-quit, 1 day post-quit, and 1 week post-quit.

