Dosing for the medication regimens will follow standard dosing procedures as follows: Participants approved to take varenicline will receive one 0.5 mg pill for the first 3 days, starting 7 days prior to the target quit day (TQD). They will then use one 0.5 mg pill twice daily for the next 4 days. After the first week of study medication ramp up, participants will use one 1 mg pill twice daily until 11 weeks post-TQD. Participants approved to take combination nicotine patch and nicotine mini-lozenge treatment will receive 12 weeks of nicotine patches and nicotine mini-lozenges starting on the target quit day (TQD). Consistent with standard dosing and package insert instructions, Participants who smoke 10 or more cigarettes/day will start with a 21 mg patch for 8 weeks, and then titrate down to a 14 mg patch for 2 weeks and then a 7 mg patch for 2 weeks. Participants who smoke 5-9 cigarettes/day will be given 10 weeks of 14 mg patches and then 2 weeks of 7 mg patches. To reduce the risk of adverse effects, all participants receiving combination NRT will receive 2 mg mini-lozenges. This is a lower dose of nicotine mini-lozenges than used in standard dosing in which those who smoke within 30 minutes are given 4 mg mini-lozenges. Participants who smoke fewer than 5 cigarettes per day will not be eligible for intensive treatment with either varenicline or combination NRT.

Adverse events associated with stop-smoking treatment will be assessed at every post-cessation follow-up (3, 12, and 26 weeks post-target quit date) and at every intensive treatment quit coach counseling call with a UW-CTRI quit coach (1 week pre-quit, 1 day post-quit, 1 week post-quit). Follow-up assessors and UW-CTRI quit coaches will follow the uploaded adverse event protocol and will notify the Tobacco Care Manager of adverse events that may be study related so that the Tobacco Care Manager can inform the primary care provider of this and coordinate care as needed.

G. Detailed study procedures: recruitment and retention

[figure not shown]

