3. Post-quit attempt assessment (See uploaded Post Treatment Follow-Up assessment). Those who request smoking cessation treatment through a Care Manager will be asked to complete 10-20 minute telephone interviews 3, 12, and 26 weeks post-target-quit day and paid \$10 for these calls (this payment is low to avoid interfering with the incentive manipulation). At these follow-ups, patient self-report of smoking, treatment use, and quitting attitudes, beliefs, and experiences (including withdrawal and social support related to quitting) will be assessed, along with any adverse events that occurred since the beginning of cessation treatment. In addition, participant utilization of treatment will be assessed by tracking how many calls or visits the participant completed and how much medication they report using.

To enhance intervention fidelity, intervention delivery will be assessed via supervisory review of recorded motivational interventions by the Care Manager and smoking cessation counseling calls delivered by UW-CTRI Health Counselors, with feedback regarding performance to enhance fidelity, as needed.

To enhance follow-up interview and visit completion rates, participants will be texted, mailed, sent MyChart reminders or automated phone calls (depending on their communication preferences as noted in the EHR and during enrollment).

Data management, transmission and storage

Data will be transferred from the EHR to research databases for use in tailoring and personalizing outreach (as randomly assigned) and tracking recruitment, participant healthcare utilization, smoking cessation treatment, and changes in smoking status, insurance type, or health status over the course of the 2-year study. Both healthcare systems maintain secure, HIPAA-compliant electronic health records for their operations and have mechanisms and processes in place to extract and encrypt data from the EHR for research purposes. Staff at UW-CTRI will receive data on enrollees who have provided consent for such data sharing as

part of the oral consent process. The data to be extracted from the EHR for the purposes of reach-focused interventions and assessment are shown in the uploaded List of EHR Data to Be Extracted. The research office will also receive data from the Wisconsin Tobacco Quit Line regarding services those in Standard Care received (i.e., did they complete the counseling call, were they sent any smoking cessation medications).

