Communication with patients via the MyChart patient portal will likewise be conducted in HIPAA-compliant ways that conform to healthcare system standards. A unique study ID will be used to store all data on individual participants and information linking that study ID to participant identifying information will be maintained by the data manager. Data being used for analysis will be identified with the study ID only. Participant contact information will only be available to study staff having direct contact with participants. Data will be stripped of direct identifiers (limited datasets) or completely de-identified prior to sharing with others outside the IRB-approved research team.

To protect against violations of privacy, patients will first have the option to opt out of the program, at study launch and quarterly thereafter, at the clinic. Those who opt out will not receive a call from a Tobacco Care Manager for recruiting and offers of smoking cessation treatment. In addition, potentially sensitive information from the EHR (e.g., depression or substance use status) will not be used to tailor automated outreach letters among those who consent to participation in this study. Only demographic and care team information will be used for tailoring and personalization.

If, in the course of the study, participants reveal important clinical information to their Tobacco Care Manager (e.g., during motivational intervention calls), the Care Manager, who will be an employee of the healthcare system, will be able to communicate directly with the patient's

primary care team (e.g., if a patient notes that they are coughing up blood) via the EHR and will advise the patient to seek care from their care team or emergency care, as appropriate.

Routine adverse event assessment will not occur in this study, except in the context of smoking cessation treatment episodes, given the minimal and informational nature of the health system reach interventions and research assessments. Adverse events that occur during smoking cessation treatment will be assessed during post-quit-day follow-ups (3, 12, and 26 weeks post-quit day). Adverse events reported by patients will be assessed fully and reported to the IRB, the host healthcare system, and if appropriate (i.e., if serious or necessitating a change in the protocol) to the study sponsor and FDA, in a timely manner, as specified by pertinent guidelines and regulations.

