
To facilitate participant safety, all study participants will receive no less than access to standard of care smoking cessation care. Those who do not meet eligibility criteria for enhanced pharmacotherapy (combination NRT or varenicline) or do not consent to such treatments, will be referred to a quit line that administers evidence-based cessation counseling and NRT monotherapy. State and national quit lines have standing protocols for screening for medical contraindications for nicotine replacement therapy. The Wisconsin Tobacco Quit Line screens for pregnancy; recent heart attack, stroke, or transient-ischemic-attack; rapid/irregular heartbeat requiring lifestyle modification or medication; severe or worsening angina; and past negative reactions to NRT, and has a standard protocol for addressing adverse events. Those who initiate intensive C-NRT or varenicline treatment (which is subject to primary care provider review) will be counseled in proper use of the medication, monitored for adverse events, and

advised to reduce or stop medication if treatment-related adverse events occur. Any adverse events reported during contact with a Tobacco Care Manager or during follow-up assessments will be fully assessed, addressed, and reported promptly to the PL and PIs, and, if study-related, to the DSMB, the IRB, and, if serious or necessitating protocol changes, NCI. Should either excessive risk to study participants and/or convincing evidence of lack of measurable benefit to study participants be determined, the study will be stopped and all participants notified in a manner appropriate to the nature of the risk and/or lack of benefit. When taking that step, the investigators will consult with the IRB and NCI.

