complete virus scan of all workstations also takes place once a week. Server system log files are scanned for unusual activity, which is immediately investigated. Network and Server Administration staff members apply critical and non-critical patches as needed. In addition, the UW-CTRI and the UWSMPH Department of Medicine also have multiple mechanisms for preserving confidentiality of research participants and providing data security in the transfer of data from participant machines to the SFTP server. The Department of Medicine web servers use Secure Socket Layer (SSL or https) technology to encrypt data exchanged between the client and the server. In addition, all online and offline components of the data systems described in the proposal will be accessible only through a login and password unique to each user. The security access levels for these login accounts are tiered and the features and privileges given to each staff member will be determined by the PIs and UW-CTRI IT Manager. To further protect confidentiality, only the UW-CTRI IT Manager will be permitted to transmit data to the SFTP server. Finally, the Department of Medicine employs extensive data backup and server redundancy procedures and performs full backups to tape weekly of all servers, along with incremental and daily backups.

Data and Safety Monitoring Committee. In addition to the protections outlined in the DSMP (above), all research activities conforming to the NIH definition of a clinical trial will also have an independent Data Safety and Monitoring Committee (DSMC). This application includes a Phase III clinical trial using communication and motivation strategies with strong theoretical rationales and promising empirical support in human research, and offering FDA-approved smoking cessation therapies prescribed in a manner consistent with FDA-approved labeling. The DSMP specifies overall monitoring that will be conducted by the PI, including timely reporting of AEs and SAEs. Every 6 months, the DSMC will convene to review the overall safety data, as well as data on safety summarized by treatment condition. As per NIH guidelines, the objective of these reviews will be to determine whether continued conduct of the trial poses any undue risk for participants.

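### Adverse events are asked about at up to six contacts per treatment round in intensive treatment but three in standard care, which can inflate the intensive rate in by-condition safety summaries.

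*Combined protocol and SAP*

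**What the plan says.** - **Shared contacts.** Section III.B (Consent): "Adverse events will be assessed among all those who initiate stop-smoking treatment at phone follow-up interviews 3, 12, and 26 weeks post-target quit date".
- **Extra contacts, intensive only.** The same section adds that these "will be assessed among those in intensive treatment during the quit coach counseling calls 1 week pre-quit, 1 day post-quit, and 1 week post-quit". Section III.F repeats this: they are assessed "at every intensive treatment quit coach counseling call with a UW-CTRI quit coach".
- **Look-back.** The Assessment Plan, item 3 (Post-quit attempt assessment), has the shared interviews cover "any adverse events that occurred since the beginning of cessation treatment".
- **Use.** The Data and Safety Monitoring Committee paragraph has the committee meet every 6 months to review overall safety data and "data on safety summarized by treatment condition", to decide whether continuing poses undue risk.
- **A different statement of the schedule.** Section H, on minimizing risks, says: "Adverse events that occur during smoking cessation treatment will be assessed during post-quit-day follow-ups (3, 12, and 26 weeks post-quit day". It does not mention the coach calls.
- **Capture in either condition.** The Data Safety and Monitoring Plan says: "Any adverse events reported during contact with a Tobacco Care Manager or during follow-up assessments will be fully assessed".

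The documents do not restrict the by-condition summary to shared contacts, define its denominator, or allow for the number of contacts.

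**The concern.** When people are asked more often, more events are recorded. The three extra prompts come with the intensive condition itself: under section III.B the coach calls are open even to intensive participants who are ineligible for medication or decline it. If true risk were equal and recall or interview completion imperfect, the extra prompts could only push the recorded intensive rate upward.

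The committee reads these summaries to judge risk, and the Data Safety and Monitoring Plan provides for stopping the study if excessive risk is found. The revised sample is 240 to 300, or 120 to 150 per level of the fourth factor. Only those who start treatment are asked, so event counts will be small. The committee would have no like-for-like table to help it tell a real excess from more frequent asking.

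**Working it through.** The plan gives no adverse event rate, adverse event sample size or safety comparison, so there is no figure to reproduce.

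**Contacts per round.** Standard: 3 (weeks 3, 12, 26). Intensive: 3 + 3 = 6, if all coach calls are completed. Over the maximum of four rounds: 12 against 24.

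**Model (assumed).** True risk is equal, and each contact that covers an event elicits it independently with probability *s*. An event covered by *k* contacts is recorded with probability 1 − (1 − *s*)^*k*. The documents give no value for *s*, so a range is shown.

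**How many contacts cover an early event.** The first coach call is a week before the quit day. Under III.F varenicline starts 7 days before the quit day and combination NRT on it, so this call falls at or before first dosing and can hardly elicit an on-treatment event. The shared interviews look back to the start of cessation treatment, so all three cover an early event in either condition.

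Ratios, intensive to standard, with follow-up complete:

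| Event arises | Prompts | *s* = 0.3 | *s* = 0.5 | *s* = 0.7 | *s* = 0.9 |
|---|---|---|---|---|---|
| Between first and second coach calls | 5 vs 3 | 0.832/0.657 = 1.27 | 0.969/0.875 = 1.11 | 0.998/0.973 = 1.03 | 1.00 |
| Between second and third coach calls | 4 vs 3 | 0.760/0.657 = 1.16 | 0.938/0.875 = 1.07 | 0.992/0.973 = 1.02 | 1.00 |
| After the third coach call | 3 vs 3 | 1.00 | 1.00 | 1.00 | 1.00 |

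**Effect on the whole rate.** Suppose 60% of events are early and get one or two extra prompts, and the other 40% are covered by two interviews in both conditions (assumed).

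- *s* = 0.5, standard: 0.6 × 0.875 + 0.4 × 0.75 = 0.825. Intensive: 0.6 × 0.938 + 0.3 = 0.863, or 0.6 × 0.969 + 0.3 = 0.881. Ratio 1.05 to 1.07.
- *s* = 0.3, standard: 0.6 × 0.657 + 0.4 × 0.51 = 0.598. Intensive: 0.6 × 0.760 + 0.204 = 0.660, or 0.6 × 0.832 + 0.204 = 0.703. Ratio 1.10 to 1.18.

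**Missed contacts.** Here *s* combines being reached and reporting the event. The Analysis Plan expects 25% of follow-up data to be missing. If that applied independently to every contact (assumption), 0.5 when asked becomes 0.5 × 0.75 = 0.375. The first two rows of the table then give 0.905/0.756 = 1.20 and 0.847/0.756 = 1.12.

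**Rounds between weeks 3 and 12 at a committee meeting.** Only one shared interview has taken place. At *s* = 0.5:

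- event already present at the first coach call, 4 vs 1: 0.938/0.5 = 1.88;
- event between first and second calls, 3 vs 1: 0.875/0.5 = 1.75;
- event between second and third calls, 2 vs 1: 0.75/0.5 = 1.50.

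Before week 3, standard care has had no scheduled prompt and no ratio can be formed.

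**Shared interviews only.** Three prompts against three gives a ratio of 1.00 at any *s*, provided interview completion is equal.

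**The case against.** A reader might infer that six contacts against three roughly doubles the recorded rate, or that an early event gets four prompts against one (ratio 1.9 at *s* = 0.5, 2.5 at 0.3). The documents do not support that as the general case. The look-back gives standard care three chances at an early event, and the first coach call comes too soon to count for most on-treatment events. Four against one is at most a snapshot of rounds between weeks 3 and 12.

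A reader might also infer that a planned safety comparison is biased. The Analysis Plan contains no adverse event endpoint, test or between-condition estimate. What is affected is how the committee reads descriptive summaries.

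Three further objections have force:

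- **True rates may differ.** Intensive treatment offers 12 weeks of varenicline or combination NRT; the quit line supplies 2 weeks of a single nicotine product. The reach interventions may also change who starts treatment. Neither is an ascertainment effect.
- **Unseen material.** Tabulation rules may be in the separate adverse event protocol or a committee table specification that is not among these documents.
- **Closer questioning of people given study-supplied medication is ordinary safety practice.** That is right, and nothing here argues for asking less.

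These points reduce the size and certainty of the problem. They do not remove it: the prompting is unequal, its direction is known, and no like-for-like summary is specified.

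**Conclusion.** The point stands as a low-severity improvement. Unequal prompting can inflate the recorded intensive rate. For an event arising between coach calls, the ratio is about 1.07 to 1.11 at *s* = 0.5 and 1.16 to 1.27 at *s* = 0.3, and negligible if nearly every contact elicits the event. The figure of about 1.9 at 0.5 is an upper bound confined to rounds not yet at week 12.

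This rests on assumed detection probabilities, independence between contacts, completed coach calls, and a committee summary that separates intensive from standard treatment. If missed interviews cluster in the same people, the independent-contact model does not size the effect. An observed difference by condition could reflect medication, who starts treatment, ascertainment, or a mixture.

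**What to change.** 1. Keep the full by-condition safety data. Add a by-condition adverse event table built only from the week 3, 12 and 26 interviews, with treatment rounds initiated as the denominator. Show how many rounds have completed each interview, so that incomplete rounds are visible.
2. Show events reported at coach calls separately by condition, and keep all of them in individual safety review.
3. Reconcile the schedule in section H, which names only the three post-quit interviews, with sections III.B and III.F.

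The cost is one extra table and a wording correction. The small downside is that an event reported only at a coach call is absent from the like-for-like table, though it remains in the full data and the separate listing. No safety question is dropped.
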